The whole task, including instructions, lasts for about 40 minutes. Immediately after completion of the task, participants are debriefed that we programed the computer to provide rigged feedback in some trials. In addition, during consent/assent, participants are told that some tasks or games may have misleading information. They are told they can elect not to participate in tasks/games with misleading information if they tell us they are opting out of any such games. Of course, as with all our tasks, participants may stop the task at any time. During debriefing, we explain that the misleading information was necessary to study how people react to frustration and how their attention and cognitive ability is influenced by the feelings of frustration. For some subjects, a version of the Stop/Change Task will be completed in the home. These subjects will view the task on a computer, and the subjects will complete a version of the task suitable for delivery in the home.

7.5.2.10.2.1. fMRI and M/EEG Acquisition: Parameters will be identical to those used in the attention paradigm.

7.5.2.10.3. Mobile Version of Inhibitory Control Tasks: We seek to develop a mobile version of the AXCPT and Stop/Change tasks, that will parallel the lab version structurally. The aim is to collect data on inhibitory control performance in a naturalistic setting and learn about these functions in daily lives. Participants will download a smartphone application for the task either on their personal smartphone or on a password-encrypted mobile device provided by the NIMH and will complete the task either in the lab or *in vivo*, or both. All behavioral data collected will be deidentified and will not be stored on the mobile device. Subject data will be extracted to Firebase, a cloud service that is managed by the NIMH; each subjects' data will be associated with a unique five-digit identification code and exported as a comma-separated value (CSV) data file. Ultimately, the remote nature of inhibitory control application has the potential to make data collection easier, for both researchers and participants, lead to more diverse samples, and increase the ecological validity of inhibitory control research.

7.5.3. Treatment (optional):

7.5.3.1. Overview: Youth can choose open treatment with either fluoxetine or psychotherapy. Adults can only receive open treatment with fluoxetine.

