In the initial phase of the current protocol, 30 children were randomly allocated to receive training in directing their attention to happy cues. This training procedure generated no evidence of efficacy, and there is a need to revise the training procedures. In another, recently published study of attention-retraining with anxious children,99 participants were trained to avoid threat. In this second study, only children with a preexisting bias received training; children without an attention bias were not enrolled, due to concerns about adverse effects in children receiving no other treatment. This study demonstrated efficacy of this training regimen, delivered as a stand-alone treatment. In the second phase of the current study, we used these same training procedures, delivered over eight weeks, in tandem with CBT. These procedures were completed in 75 children, approximately half of whom received the active form of attention-retraining (attention bias modification treatment [ABMT]) and half of whom received the placebo training. The analysis of these data showed a substantial benefit on anxiety symptoms in children and adolescents with an anxiety disorder receiving Cognitive Behavioral Therapy (CBT). However, evidence of differential efficacy of CBT was equivocal; a consistent pattern of differences did not emerge between subjects receiving active and placebo ABMT. Of note, we have found that effects of ABMT can vary based on participant engagement in the training, as quantified with a reaction-time (RT) measure and that individuals with anxiety tend to show less engagement than individuals without anxiety based on such RT-based measures (see Abend et al. 2013). For subjects in the current protocol, we did find that our RT-based measure of training did not differ among subjects randomized to the two treatment conditions. This suggests that our failure to demonstrate an enhanced effect of active relative to placebo ABMT could reflect insufficient engagement in ABMT. In the third phase of this protocol, the hope is that with better engagement, we can find a beneficial effect in a subsequent trial of 120 subjects. Before beginning the next randomized controlled phase of this protocol, we piloted the procedures for active ABMT, to make sure that we can achieve acceptable levels of training, as quantified by our reaction-time-based measure. Ten participants completed the ABMT pilot. As a group, these participants showed good accuracy on the behavioral paradigm (mean = 86.29%) and performed at an expected speed (mean reaction time = 492.81 ms). This demonstrates acceptable data to move forward with the randomized phase of the training experiment. Change in reaction time was examined across the blocks of the task to examine online learning. Eight of the ten participants showed improvements in reaction time through online training, which was statistically significant even in this small sample (mean improvement = 28.43ms, t = 3.07, p = .009). This is superior relative to our prior procedure, which again demonstrates acceptable data to move forward with the randomized phase. Participants will be randomized into active and placebo conditions, and the procedures for the trial will be identical to phase two.

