KEY FOR ABBREVIATIONS IN TABLE APPEARING ABOVE: "KSADS" full- Complete Kiddie SADS; partial-anxiety and depressive modules of K-SADS; "FHE"-Family History Evaluation; "Demographics"-Demographic Interview; "SCARED"-Self-Report for Childhood Anxiety Related Disorders; "CGI"-Chinical Global Impressions (Severity and Improvement); "PARS"-Pediatric Anxiety Rating Scale; "ARI" – Affective Reactivity Index; "CBCL"-Children's Behavior Checklist Internalizing Scale; "CDRS-R"-Children's Depression Rating Scale; Revised; "CGAS"-Children's Global Assessment Scale; "HARS"-Hamilton Anxiety Rating Scale; "Adverse Events"-Fluoxetine Side Effects Scale; "Therap"-trained non-medical researcher or social worker, RA-research assistant, MD-child psychiatrist or pediatrician; P-parent; C-child.

7.5.3.3. Assessments: As shown above, adverse events are rated weekly. The primary efficacy measure comprises the CGI-Improvement rating, as this measure detected a significant effect of SSRIs on mood and anxiety disorders in both Emslie et al.³⁶ and the RUPP Anxiety Group Trial. Clinician ratings of anxiety and depressive symptoms are also completed weekly. Anxiety is rated with the Psychiatric Anxiety Rating Scale (PARS),⁸⁶ which detected a strong treatment effect of an SSRI on anxiety in the RUPP Trial. Depression is rated on the Children's Depression Rating Scale (CDRS), which detected a strong treatment effect of fluoxetine in Emslie et.al.³⁶ The Affective Reactivity Index (ARI)¹⁴⁵ will also be completed to assess clinican-, parent-, and child-rated irritability. The CGI Severity index is also completed weekly;^{84, 85} it also detected a strong treatment effect in both studies. Other measures are assessed, beyond these main outcome measures, to detect clinical efficacy. These are assessed at randomization, week-4, and termination; they include: i) three self-rated scales, the SCARED,⁸³ MASQ,⁹⁰ and CDI,⁸⁷ and/or MFQ ii) the HARS and HAM-D;⁸⁹ and iii) the CGAS.⁸⁸

7.5.3.4. Dosage for Medication: A flexible titration schedule is used, such that 10 mg of fluoxetine is given in week-1, followed by 20 mg from weeks 2-4; the dose can be raised by 10 mg in week five and 10 mg in week six for children who remain symptomatic. In addition, dose can be lowered for children who develop side effects.

7.5.4. Follow-up/Termination Procedures:

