Subjects will be removed from the study by the research team under three circumstances. First, in each instance where a subject shows clinical worsening or clinically significant adverse events, details of the case will be reviewed independently by three clinicians during the first visit where the subject shows worsening as well as the next visit. Results of this review will be discussed with the patient and families. Clinical worsening is defined as a rating of "7" ("worse") or greater on the CGI-I for any visit. Subjects will be removed from the study if they are rated as "worse" by two of the three clinicians for two consecutive weeks, though families are free to discontinue the trial at any point. Second, subjects will be removed if they exhibit clinically significant increase in suicidal ideation.

10. Outcome Measures:

The main outcome measures, related to the primary study goals, derive from the fMRI paradigms. These measures represent indices of percent-signal change in hypothesized brain regions, comprising amygdala, striatum, and prefrontal cortex (PFC). In each fMRI paradigm for each of these brain regions, a measure of percent-signal change is generated for the main study contrast for each paradigm. These percent-signal change measures are also used as predictors in analyses related to secondary study goals. Similar neural activity data will be obtained using MEG.

One set of key secondary outcome measures derives from the treatment-response data. Treatment response is defined based on one categorical measure and one continuous measure. The categorical measure is the Clinical Global Improvement (CGI) score, and the continuous measure is the Pediatric Anxiety Rating Scale score (PARS). Other assessment measures collected during treatment (e.g., parent or child ratings on symptom scales) serve to augment the main analysis, based on the CGI and the PARS.

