in anxiety symptoms and higher rates of response. To test this hypothesis for continuous outcome measures, we will contrast study groups, defined by attention-training conditions, using random effects regression (for continuous measures)⁹⁵ or using logistic regression (for dichotomously-defined CGI outcomes). Parallel logistic regression models will be used to predict treatment response, defined as a CGI rating that is better than "4" (4=minimally improved). This hypothesis is tested as the main effect of treatment group on CGI category (responder vs. non-responder). In all analysis, the intent-to-treat principle will be used, such that all available data from all randomized subjects will be included.

For continuous measures, each dependent measure (Y_j) is predicted by the following model: $Y_j = \beta_{lj} + \beta_2 T + \beta_{3j}T + \beta_4 I + \beta_5 TI + \beta Z + \varepsilon_{ij}$ where I indicates treatment status; j indexes subjects; T indexes time (for repeated measures); β_{1j} is a random effect for the intercept of the jth subject; β_2 is the average slope; β_{3j} is a random effect for the slope of the jth subject; β_4 is treatment status; β_5 is the difference in slopes over time between groups specified in β_4 . βZ is the effect of possible covariates (e.g., child's age or diagnosis), and ε_{ij} is a random effect for error. We will assess significance of β_5 (group-by-time interaction) to evaluate effects of sham/active attention training on symptoms. Of note, the Pediatric Anxiety Rating Scale (PARS) will serve as the primary outcome measure in this analysis. However, secondary outcome measures will include measures of self and parent reported symptoms as well as reports of symptoms collected on EMA technology. Secondary analyses will examine moderation of treatment response based on the behavior of the therapist during CBT. This behavior will be quantified whereby the methods from Ewbank et al.¹⁶¹ will be used to classify therapist behavior. This will require transcription of therapist speech to the patient during therapy and classification of this speech using machine learning to determine if features found to predict CBT response by Ewbank et al. also predict CBT response in the current protocol.

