With sample sizes of n=45, statistical power is adequate (β >0.80) for detecting differences between patients and comparisons, assuming medium-to-large effects (standardized difference [*d*]=0.8-1.2).⁹⁶ Such effect sizes have typically emerged in prior studies documenting hypothesized between-group differences in psychological function or fMRI activation. This includes prior studies in both adults and in youths. Moreover, we expect to see similar differences in youths and adults, and our prior studies in both groups find between-group differences of this magnitude. Thus power will be adequate to test all of our primary hypotheses concerning both fMRI and neuro-cognitive differences between patient groups and healthy adolescents as well as our secondary hypotheses on comparable differences in adults. For any comparison where a cell contains less than 45 subjects (e.g. subjects with major depression but not an anxiety disorder), power will be less than adequate. These data will be used to generate estimates of effect sizes to consider the feasibility of conducting further studies in such relatively select subject groups. Finally, for treatment effects, based on prior work in this protocol, we expect a medium effect separating patients receiving CBT randomized to active and placebo forms of treatment. Therefore, the plan is to include 120 subjects in the RCT, with 60 randomized to the active form of ABMT and 60 randomized to the placebo form of ABMT.

12. Human Subjects Protection:

12.1. Subject Selection:

This study examines brain structure and function in psychiatrically healthy as well as clinically anxious or depressed children, adolescents and adults. For healthy subjects, volunteers will be solicited, as prior studies performed at the NIH on developmental aspects of brain structure document the feasibility of this approach.^{97, 98} Impaired subjects will be recruited when they present for treatment. Sample sizes for the current project derive from power considerations in the proposed fMRI and treatment studies. In general, power in the proposed fMRI studies will be adequate to detect large effect sizes with n=15. Assuming that acceptable data will be generated from approximately 90% of studies, the proposed sample size will allow us to obtain data in 15 subjects for each relevant group of subjects.

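### The plan does not settle whether PARS or CGI-Improvement decides the active-versus-placebo ABMT comparison, and it credits its assumed medium effect to prior work that reports no such effect

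*Combined protocol and SAP*

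**What the plan says.** Three sections of the combined protocol and SAP speak to the deciding outcome.

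- Section 7.5.3.3 (Assessments): "The primary efficacy measure comprises the CGI-Improvement rating". The reason given is that this rating detected SSRI effects in earlier trials.
- Section 10 (Outcome Measures) defines treatment response by one categorical measure, the CGI, and one continuous measure, the PARS. Other ratings "serve to augment the main analysis, based on the CGI and the PARS". Both are classed as key secondary measures for the protocol as a whole.
- Section 11.3 (Clinical Data) states the hypothesis that active training gives larger symptom reductions and more responders than placebo. For the random-effects model, "the Pediatric Anxiety Rating Scale (PARS) will serve as the primary outcome measure in this analysis", tested by the group-by-time coefficient (beta5). For the logistic model, "This hypothesis is tested as the main effect of treatment group on CGI category (responder vs. non-responder".

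On size, section 11.5 says that "based on prior work in this protocol, we expect a medium effect separating patients receiving CBT randomized to active and placebo forms of treatment" and concludes that 120 subjects will be randomized, 60 per arm. It gives no outcome, numerical effect, alpha or power for this comparison.

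The prior work is described in section 7.5.3.1. Phase 1 (30 children) gave no sign of benefit. In phase 2 (75 children), "evidence of differential efficacy of CBT was equivocal; a consistent pattern of differences did not emerge" between active and placebo ABMT. The ten-participant pilot used active training only. Phase 3 rests on the hope that better engagement will bring out an effect.

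**The concern.** A randomized comparison needs one stated basis for calling it positive. Here a reader of 7.5.3.3 would look to CGI-Improvement, a reader of the continuous model in 11.3 would look to PARS, and a reader of section 10 would look to both. If one test is significant and the other is not, the plan does not say what follows. The choice could then be made with the results in hand, and a nominal 5% error rate would no longer describe the procedure. Since phase 2 ended without a consistent pattern, a mixed result in phase 3 is a realistic prospect.

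The wording of 11.5 is a second, related problem. By attributing the medium effect to prior work in this protocol, it presents an assumption as though it had been observed.

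**Working it through.** **1. The passages side by side.** There are two instruments and three designations: CGI-Improvement (7.5.3.3), the CGI and PARS without order (10), and PARS in the continuous model with CGI response tested alongside (11.3). Sections 10 and 11.3 can be read together as one continuous and one categorical analysis. Section 7.5.3.3 cannot be reconciled with PARS as primary. No section gives a hierarchy, a multiplicity adjustment or a rule for discordance.

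**2. The plan's own figure.** 60 per arm cannot be derived from stated inputs, because none are given for this comparison. With n = 2(z_a + z_b)²/d² per arm, and assuming d = 0.5, two-sided 0.05 and 80% power: n = 2(1.960 + 0.842)²/0.25 ≈ 63 (64 with the t distribution). That is close to 60 but does not reproduce it.

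**3. False-positive rate if either outcome counts.** The rate is 1 − P(|Z1| < 1.96 and |Z2| < 1.96), with Z1 and Z2 bivariate normal under the null.
- Independent tests: 1 − 0.95² = 9.75%.
- For correlated tests, assume a PARS-CGI correlation of 0.5-0.9 on the underlying scale and 40-60% response. Dichotomising multiplies the correlation by φ(z)/√(p(1−p)), which is 0.386/0.490 = 0.789 at 40% or 60% and 0.399/0.5 = 0.798 at 50%. The test statistics then correlate between 0.5 × 0.789 = 0.39 and 0.9 × 0.798 = 0.72.
- Correlation 0.39: 9.3%. Correlation 0.50: 9.1%. Correlation 0.72: 8.3%.

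**4. Power at 60 per arm** (assumed: two-sided 0.05, no loss, single time point).
- PARS, d = 0.5: noncentrality 0.5 × √(60/2) = 2.74; normal approximation Φ(2.74 − 1.96) = 78.2%; noncentral t 77.5%.
- CGI response, if the same 0.5 SD shift is dichotomised: the active rate is Φ(Φ⁻¹(p0) + 0.5). Placebo 40%, 50% and 60% become 59.7%, 69.1% and 77.4%, with power 58%, 57% and 54%.
- CGI response, if medium is taken as Cohen's h = 0.5: placebo 40%, 50% and 60% become 64.7%, 74.0% and 82.3%, with power 78%, 78% and 77-78%.

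Power on CGI response thus depends on how a medium effect is translated, and the documents do not say.

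**5. What phase 2 could show.** Assuming 38 and 37 per arm, the 95% half-width for a standardized difference is 1.993 × √(1/38 + 1/37) = 0.46 SD. A trial of that size with no consistent difference neither establishes nor excludes d = 0.5.

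**The case against.** The best defence is that 7.5.3.3 is residual text. It argues from SSRI trials and is followed directly by fluoxetine dosing, whereas 11.3 is where the ABMT hypothesis is stated and tested. Nor does the phrase "These are assessed at randomization, week-4, and termination" tie CGI-Improvement to the randomized phase, because it refers to the other measures in that paragraph. Much of this stands. But the sentence is current text, and treatment itself is not randomized ("Youth can choose open treatment with either fluoxetine or psychotherapy"), so ABMT is the only randomized comparison among treated patients to which a primary efficacy measure could apply. Even with 7.5.3.3 set aside, 11.3 leaves two tests of one hypothesis and no rule between them.

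A second defence is status. Section 5 makes ABMT an additional secondary goal that will yield preliminary data. That stands and lowers the severity. It does not remove the need to say which test decides, since 11.3 specifies a directional hypothesis, significance testing and intention-to-treat.

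Some stronger readings are tempting but not supported:
- That there are three different outcomes. There are two instruments.
- That a PARS-only result is positive by 11.3 and negative by 7.5.3.3. Section 11.3 also tests CGI response, so its verdict would be unclear rather than positive.
- That 60 per arm is too few. The apparent power gap on CGI response comes from one modelling choice and disappears under h = 0.5.
- That 11.5 contradicts itself by saying sample sizes are not informed by treatment effects. It goes on to treat the randomized trial separately.

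**Conclusion.** The concern holds as an inconsistency in designation. The deciding outcome for active versus placebo ABMT is stated differently in 7.5.3.3, 10 and 11.3, with no rule for a split result. If either test at 0.05 may count, the error rate is about 8-9% (9.75% at independence) instead of 5%. That figure rests on an assumed test correlation of 0.4-0.7 and on an either-counts reading, which the plan neither adopts nor rules out.

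The medium effect in 11.5 is a planning assumption. Phase 1 and phase 2 do not supply it, although a reader should not infer that phase 2 disproves it. Under d = 0.5 the trial has about 78% power on PARS before any gain from baseline adjustment or repeated measures and before any loss to follow-up. On CGI response it has between 54-58% and 77-78%, depending on the definition of medium. The missing numerical inputs are an omission of detail, not evidence of an inadequate trial.

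Severity is moderate, because the randomized trial is a secondary goal.

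**What to change.** Before phase 3 is unblinded:

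1. Name one primary outcome and one test for the ABMT comparison. Section 11.3 already supports PARS with the group-by-time coefficient beta5.
2. On that choice, amend 7.5.3.3 and section 10 so that CGI-Improvement response is a secondary outcome that cannot by itself make the trial positive.
3. Reword 11.5 so that the medium effect is given as an assumption resting on better engagement with the training, not as a finding of prior work.

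This is a change of text only. N=120 stays and no patients are added. The price is that the trial can no longer claim success on CGI-Improvement alone.

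### Does the 60-per-arm attention-training trial need a new sample-size rationale because the protocol's earlier phases did not show the medium effect it cites?

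*Combined protocol and SAP*

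**What the plan says.** Section 11.5 (Sample Size Justification) closes with the attention-training trial. It states that "based on prior work in this protocol, we expect a medium effect separating patients receiving CBT randomized to active and placebo forms of treatment", and concludes that "the plan is to include 120 subjects in the RCT", 60 to each form of training. It attaches no standardized difference, PARS difference, standard deviation, alpha, power or dropout rate to that statement. The nearest figures in the section concern a different question, the patient-versus-comparison contrasts at n=45. Those are powered "assuming medium-to-large effects (standardized difference" 0.8 to 1.2).

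Section 7.5.3.1 (Treatment, Overview) describes the earlier work:

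- **Phase 1** (30 children) trained attention towards happy cues: "This training procedure generated no evidence of efficacy, and there is a need to revise the training procedures".
- **Phase 2** (75 children, about half on active training, all with CBT): "evidence of differential efficacy of CBT was equivocal", and "a consistent pattern of differences did not emerge between subjects receiving active and placebo ABMT". The investigators suggest that "our failure to demonstrate an enhanced effect of active relative to placebo ABMT could reflect insufficient engagement in ABMT".
- **Pilot** (10 participants): "we piloted the procedures for active ABMT". Accuracy and reaction time are reported, and online learning is described as better than under the previous procedure.

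Section 11.3 makes the PARS group-by-time term the primary test of active against placebo training. Section 5 lists this comparison as an additional secondary goal that will yield preliminary data.

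**The concern.** Read together, the two sections seem to disagree. Section 11.5 derives the trial's size from an active-versus-placebo effect credited to this protocol, yet no phase in section 7.5.3.1 supplies one. Phase 1 found nothing. Phase 2 is described as a failure to show an added effect, and its substantial benefit was seen in children receiving CBT, which both arms get. The pilot had no control arm. The one positive trial mentioned there was an outside study of stand-alone training.

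The word *medium* is also left without a number, in a section that labels 0.8 to 1.2 as medium-to-large. If the true difference were well below a conventional medium effect, 60 per arm would be too few, and a null result could be over-read. With an assumed two-sided alpha of 0.05 and a t test, power would be 58% at d=0.4 and 37% at d=0.3.

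**Working it through.** **Inputs from the documents:** 120 children, 60 per arm (section 11.5); phase 2 size 75, about half per arm (section 7.5.3.1).

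**Assumptions not in the documents for this trial:** two-sided alpha 0.05, an unadjusted two-sample comparison at one time point, no attrition, and a 37/38 split in phase 2. *Medium* is varied, with d=0.5 as the central reading.

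**1. Can the plan's figure be reproduced?** Not strictly, because no d, alpha or power is stated. The question is which d fits 60 per arm.

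Detectable d = (1.960 + z for power) × √(2/60), where √(2/60) = 0.1826.

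- 80% power: (1.960 + 0.842) × 0.1826 = 0.51 (t test 0.52).
- 90% power: (1.960 + 1.282) × 0.1826 = 0.59.

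**2. Power of 60 per arm.** Power ≈ Φ(d × √(60/2) − 1.960), where √30 = 5.477.

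| d | Normal approximation | t test |
|---|---|---|
| 0.3 | 38% | 37% |
| 0.4 | 59% | 58% |
| 0.5 | Φ(2.739 − 1.960) = 78% | 78% |
| 0.6 | 91% | 90% |
| 0.8 | 99% | 99% |

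**3. Size needed for 80% power.** n per arm = 2 × (1.960 + 0.842)² / d² = 15.70 / d².

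- d=0.5: 15.70 / 0.25 = 62.8, so 63 (t test 64).
- d=0.8: 15.70 / 0.64 = 24.5, so 25 (t test 26).

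A planner who meant 0.8 would have needed fewer than half of the 60. The chosen size points to d of about 0.5 to 0.6, so the term is less ambiguous than it looks.

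**4. What can phase 2 rule out?** The 95% half-width on d is about 1.96 × √(1/37 + 1/38) = 1.96 × 0.231 = 0.45.

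- An observed d below 0.50 − 0.45 = 0.05 would exclude 0.5.
- An observed d above 0.45 would exclude zero.
- Anything between is compatible with both.

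Phase 2 had only about 57% power for d=0.5 (t test, 37.5 per arm). A missed medium effect would have been unremarkable.

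**5. Do the two sections conflict?** Phase 1 tested a different intervention: happy-cue training, whereas the planned trial trains attention away from angry faces. It says little about the effect now expected. Phase 2 is reported without an estimate, so it neither supplies nor refutes a medium effect. The pilot gives no symptom contrast, but it is in-protocol evidence for the stated reason to expect more than phase 2 showed, namely better engagement. Section 7.5.3.1 ties the trial of 120 to that reason, and the training is now embedded in a video game for it.

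**The case for a change.** The best case for a change is that saying an effect is *based on prior work* claims more than saying it is not excluded. Section 11.3 specifies a directional hypothesis and a formal test, and section 12.5.3 warns that the training could slow a child's response to CBT or fluoxetine. On that view, anyone weighing the randomisation of 120 children should see the phase 2 estimate with its confidence interval, and the d, alpha and power intended. The cost would be a few sentences and one calculation. Dropout would lower the figures further: with an assumed 10% loss (54 per arm), power at d=0.5 is about 73% to 74%.

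Part of this stands. The attribution is not documented, and the effect size is not given as a number. Reporting the phase 2 PARS difference would make the rationale easier to judge. But the reader is not misled about phase 2, since section 7.5.3.1 states the failure and its suspected cause. Striking the attribution now would also prejudge an estimate that only the sponsor holds: a phase 2 difference near 0.4 or 0.5 would make the wording defensible. Finally, the gap between 78% and 80% rests on an assumed alpha, an assumed d and an endpoint t test, whereas the planned test is a random-effects slope comparison on a scale rated at most weeks. It does not show that 120 is too few.

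**Conclusion.** No change to the plan is needed. Section 11.5 leans on an effect that section 7.5.3.1 does not document, and it leaves *medium* unquantified. This is a thin rationale, not an inconsistency that affects the trial. The plan states no power or detectable difference that the design misses, and phase 2 was too small to exclude a medium effect unless its observed d was below about 0.05. The chosen size matches a conventional reading: about 78% power at d=0.5, and 80% at about 0.52. Filling in the missing detail would alter neither enrolment, visits, the PARS analysis nor the inference from it, for a comparison the protocol itself ranks as secondary and preliminary. Whoever reports the trial can state what 60 per arm could detect and give the confidence interval.

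These figures assume two-sided alpha 0.05, an unadjusted comparison of two means, no attrition and a near-even phase 2 split. Power for the planned group-by-time test depends on variances that the documents do not give.
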